The VA cares for approximately 40,000 veterans with SCI. In addition there are over 200,000 non-veterans with SCI in the US. Many of these individuals have neurogenic bowel and suffer from the embarrassment and social isolation caused by FI. The life expectancy of SCI patients has dramatically increased, with most SCI patients living up to 60 years of age (10 years less than non SCI patients). Given that the average age of injury is 37 years and that 25% of SCI patients are between 19 to 25 years, these individuals have to live with the ignominy of fecal incontinence for many years to come. The current practice of using multifaceted programs for bowel care leaves much to be desired, as many SCI patients still suffer from FI and constipation. In this respect it has become urgent to develop other treatment options for neurogenic bowel complications in order to improve quality of life and to preempt further GI complications/

Relevance of the proposed work to the VA patient care mission

The VA system cares for a large number of persons with SCI, and FI and time consuming and cumbersome bowel care has been identified as a major QOL issue among the veterans. Despite extensive efforts to understand its pathophysiology and numerous clinical guidelines for its management, FI and constipation remain tenacious problems that limit the social interactions of veterans with SCI. The proposed work will result in the only known data regarding the efficacy of bowel biofeedback treatment and the outcome of FI in person with SCI. Furthermore, to the extent that biofeedback treatment can improve FI, this research should be cost effective because it would prevent physical and psychological comorbidities associated with neurogenic bowel as it is far less expensive to provide bio feedback treatment than to treat chronic conditions like depression arising from social isolation, and dermatological treatments arising from exposure of the skin to FI. Providing veterans with cutting edge preventive care is a key component of the VA patient care mission.

F. LIST OF KEY BIBLIOGRAPHICAL REFERENCES

1. Devivo, M.J., *Epidemiology of traumatic spinal cord injury: trends and future implications*. Spinal Cord. **50**(5): p. 365-72.
2. Valles, M., et al., *Bowel dysfunction in patients with motor complete spinal cord injury: clinical, neurological, and pathophysiological associations*. Am J Gastroenterol, 2006. **101**(10): p. 2290-9.

Utility of an Animated Bowel Biofeedback Training Routine to Improve Bowel Function in Individuals With SCI

NCT02406859

March 10, 2013

Statistical Analysis Plan

For the continuous dependent, independent and demographic variables, descriptive statistics will be performed and expressed as group mean ± SD, with 95% confidence intervals and ranges. To examine the effect of the training on manometric and subjective parameters (groups: stratified by level of injury and completeness) analysis of variance (ANOVA) with repeated measures on visit (Pre, Post) will be performed. In the event of non-normal distribution of study outcomes, non-parametric ranking statistics will be applied as appropriate. An a priori level of significance will be set at P≤0.05. IBM SPSS Statistics version 22 will be used for all analyses.

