**Utility of an Animated Bowel Biofeedback Training Routine to Improve Bowel
Function in Individuals With SCI**

NCT02406859

October 10, 2016

STUDY TITLE: Utility of an Animated Bowel Biofeedback Training Routine to Improve Bowel Function in Individuals with SCI

A. SPECIFIC AIMS

Biofeedback techniques are known to decrease the frequency of fecal incontinence (FI) in able-bodied (AB) populations and improve reflex defecation in persons who experience constipation. We hypothesize that bowel biofeedback training in spinal cord injured (SCI) patients will result in the following:

In subjects with decreased external sphincter strength and control (FI subjects): Improved objective bowel function parameters as measured by anorectal manometry, a decrease of FI episodes, a decrease in Wexner's incontinency score and a decrease in the SCI Bowel Surveys Score.

In subjects with tonic, constricted external sphincter and missing/decreased recto-anal inhibitory reflex (RAIR) (constipation subjects): An increase in sensitivity and strength of the RAIR and decreased symptoms of constipation (Bowel and Bladder Survey).

Specific Aims:

1. To assess baseline motility characteristics (resting pressure, squeezing pressure, high pressure zone, and RAIR) in persons with chronic SCI.
We hypothesize that individuals with SCI will have abnormal resting pressures (either increased or decreased, decreased squeezing pressures and an impaired RAIR reflex.
2. To determine the characteristics of SCI (level, completeness, baseline manometric parameters) which best predict the outcome of the biofeedback training. Additionally, we aim to assess the efficacy of bowel biofeedback therapy in SCI patients in improving:
 - a) Changes in maximum rectal and sphincter pressures generated during "squeeze" and "bear down" maneuvers performed during anorectal manometric studies pre-post treatment.
We hypothesize that due to the learning and conditioning effects of the biofeedback training, we will observe increases in generated sphincter pressures.
 - b) Changes to the sensitivity and strength of response of the RAIR reflex in response to rectal distension.
We hypothesize that the RAIR response will may be partially restored or strengthened by biofeedback training.
 - c) FI and constipation as assessed by the Bowel Surveys and Wexner's Incontinence Scale.
We hypothesize that biofeedback will improve subjective symptoms of FI, constipation, or both.

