Neurogenic bowel characteristics differ among SCI individuals, and appear to depend primarily on the level and completeness of injury. It is thought that upper motor neuron lesions in the spinal cord above the conus medullaris (L1-2) results in a hyperreflexive bowel with increased colonic wall tone and loss of cortical control over the relaxation of the external anal sphincter (EAS). These changes result in chronic high sphincter tone and dyssynergic defecation. The main symptoms in these patients are constipation and fecal retention, or difficulty with evacuation (DWE). In many of these individuals, some nerve connections between the spinal cord and the colon may be preserved, and stool propulsion and reflex coordination may remain intact and under control of the central nervous system [3, 6]. Furthermore, individuals with spinal lesions above T7 experience loss of voluntary control over abdominal muscles and an inability to increase intra-abdominal pressure, which results in more DWE and constipation [2]. Lower motor neuron (LMN) lesions in the spinal cord below L1-2 result in the interruption of the centrally mediated innervation to the bowel, which causes slowing of peristalsis, a flaccid EAS, and atonic levator ani muscles. This is also called an areflexic bowel. The main symptoms in these patients are constipation from slowed peristalsis and FI from atonic EAS and levator ani muscles. While the symptoms of bowel dysfunction in persons with SCI are known, function and motility of the anal canal have not been documented in this population. Various techniques, such as the measurement of pressure profiles facilitate assessment of GI motor function. Anorectal manometry can provide valuable information about sphincter strength, defecation dynamics and reflex mechanisms. In the past few decades, motility studies have been conducted using water-perfused systems. These systems consist of a multilumen catheter which is connected to an array of pressure transducers, a pneuomhydraulic pump to provide the continuous flow of water, and a display system. The pneuomhydraulic pump drives water through very narrow channels of the catheter at a constant low rate, but under very high pressure. Each channel of the catheter is connected to a separate pressure transducer. Any interference with the flow of water from any of the various channels by lumen occluding contractions in the channel raises pressures in that channel. Pressure transducers continuously monitor pressures in the channels. This information is transmitted to a computer and displayed as line tracings. While useful, such systems are limited by the number of channels each catheter can accommodate as catheter size is limited. This greatly reduces the amount of information that can be captured, especially in small, activity-laden areas such as sphincteric regions. New high-resolution anorectal manometric systems (Given Imaging, Duluth, GA), simultaneously captures pressure data from the rectum, IAS, EAS and atmosphere. These systems allow for tight spacing of many pressure sensors, which allow visualization of short as well as long segment retrograde and anterograde contractions. Short segment retrograde contractions cannot be normally visualized using traditional manometry due

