For our pilot study, we are proposing the use of a 12 week biofeedback training to improve anorectal motility and voluntary control of the IAS, EAS and rectal musculature. It is unknown as to what level and completeness of SCI patients can expect to benefit from such treatment. As such, we are planning on enrolling all non-ambulatory SCI subjects with complete or incomplete injuries (ASIA A, B, C or D). Subjects will be enrolled only if they currently report problems with either constipation or FI on a based on survey responses (Ten Item SCI Bowel Survey (10 SCIB) and Wexner's Incontinency Scale (WIS). Anorectal motility pre to post biofeedback training will be performed. We aim to describe the anorectal pressure profile in persons with SCI and to identify responders to biofeedback training. We believe anorectal function will differ according to the level and completeness of injury. Additionally, we seek to define the levels and completeness of injury, and baseline manometric parameters which are predictors of treatment success.

C. PROCEDURES, METHODS AND EXPERIMENTAL DESIGN

This is a prospective, non-randomized, single center clinical trial. SCI patients will be stratified to 4 different arms according to the level of SCI:

- Upper motor neuron (UMN) incomplete (C5-T12)
- Lower motor neuron incomplete (LMN) (L2-S5)
- UMN complete (C5-T12)
- LMN motor neuron complete (L2-S5)

The Inclusion/Exclusion criteria are as follows:

Inclusion Criteria:

- Chronic SCI (duration over 1 year),
- Able-bodied (non-SCI)
- Between the ages of 18-75.

Exclusion Criteria:

- Contraindication to bowel biofeedback,
- Currently pregnant or trying to become pregnant,
- Inability to provide informed consent.

Study Population

Veterans from the JJPVAMC with chronic SCI, who are seen routinely in outpatient clinic and who complain of fecal incontinence or constipation (Screening Questionnaire: Appendix 1). Additional healthy AB veterans and/or non-veterans will be included in the study population as controls.

Recruitment and Enrollment:

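### The two lead hypotheses concern FI subjects and constipation subjects, but the SAP groups training outcomes only by injury level and completeness, so the reported changes are case-mix averages

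*SAP*

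**What the plan says.** **Lead hypotheses (Protocol, section A).** The first begins "In subjects with decreased external sphincter strength and control (FI subjects" and expects better manometry, fewer FI episodes and lower Wexner and bowel survey scores. The second begins "In subjects with tonic, constricted external sphincter and missing/decreased recto-anal inhibitory reflex (RAIR) (constipation subjects" and expects a more sensitive and stronger RAIR and fewer constipation symptoms. Aims 2a to 2c, further down the same section, are not split in this way; the hypothesis under Aim 2c covers either symptom or both.

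**Who is trained.** Section B states "Subjects will be enrolled only if they currently report problems with either constipation or FI". Section C (Study Population, and the end of Part 1) likewise admits either symptom, and Part 2 takes 20 subjects with incomplete injuries (ASIA B, C, D). Section C, Recruitment and Enrollment, speaks of patients with FI only.

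**Analysis.** The SAP is one paragraph. Training effects are examined by repeated-measures ANOVA (Pre, Post) on "manometric and subjective parameters (groups: stratified by level of injury and completeness". Neither document defines an FI or constipation group for this analysis.

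**Level and symptoms (Protocol, section B).** For UMN lesions: "These changes result in chronic high sphincter tone and dyssynergic defecation" and "The main symptoms in these patients are constipation and fecal retention, or difficulty with evacuation (DWE". For LMN lesions, after describing a flaccid external sphincter: "The main symptoms in these patients are constipation from slowed peristalsis and FI from atonic EAS and levator ani muscles".

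**The concern.** Each lead hypothesis names a population and the endpoints expected to improve in it. The SAP never forms those populations. A trainee who enters with constipation alone cannot have fewer FI episodes than zero, and has little room to improve on an incontinence score. The same holds in reverse for constipation endpoints. Averaging over everyone, or within injury level, gives a number that moves with the mix of symptoms enrolled. A reader could then take a small average change in Wexner score as a weak effect in incontinent subjects when it partly reflects how few of them there were. If the groups are not defined in advance, any later symptom split will be post hoc.

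**Working it through.** The documents give no effect size, SD or sample-size derivation, so there is no planned figure to reproduce.

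**1. What the SAP grouping becomes.** Two levels by two degrees of completeness make four cells. Part 2 admits incomplete injuries only, so two remain: UMN and LMN. By section B these differ in sphincter state (high tone against flaccid), but constipation is a main symptom of both. Level therefore tracks sphincter state in part and does not separate symptom type.

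**2. Dilution.** Let p be the FI share of the 20 trainees.

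All-trainee mean change = p × (change in FI subjects) + (1 − p) × (change in the others).

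Assume, for illustration only, a mean change of 0.8 SD (SD of change 1) in FI subjects and 0 on average in the others:

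- 10 of 20: 0.50 × 0.8 = 0.40 SD
- 15 of 20: 0.75 × 0.8 = 0.60 SD
- 20 of 20: 0.80 SD

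The documents do not give p. The 15% to 85% in section B describes FI across published SCI studies and is not an estimate for people enrolled for either symptom.

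**3. By level.** With FI in 8 of 10 LMN and 2 of 10 UMN trainees (assumed), the level means are 0.8 × 0.8 = 0.64 SD and 0.2 × 0.8 = 0.16 SD. Level recovers part of the split, but both figures remain mixtures.

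**4. Power and coverage.** Simulated one-sample t-test on change scores, N = 20, two-sided 5% (sidedness assumed). The result depends on how variable the change is in trainees without FI:

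| FI subjects | SD of change in the others | Power, all 20 | Power, FI subjects alone | All-trainee 95% CI contains 0.8 SD |
|---|---|---|---|---|
| 10 | 0 | 60% | 62% | 45% |
| 10 | 0.5 | 48% | 62% | 52% |
| 10 | 1 | 34% | 62% | 66% |
| 15 | 0 | 82% | 82% | 85% |
| 15 | 1 | 68% | 82% | 89% |

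Zero variability is plausible for FI episodes in someone who has none. It is not plausible for the bowel survey or squeeze pressure. The mean dilution in step 2 is the same in either case.

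**5. Price of reporting by group.** The 95% CI half-width is t(0.975, n − 1)/√n, in SDs of change:

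- n = 20: 2.093/4.472 = 0.47
- n = 10: 2.262/3.162 = 0.72
- n = 5: 2.776/2.236 = 1.24

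**6. Regression to the mean.** If the FI group were the upper half of a normal baseline score with test-retest correlation r, the expected fall with no training effect is (1 − r) × 0.798 baseline SD. The SD of change is √(2(1 − r)) baseline SD.

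- r = 0.9: 0.080 baseline SD; 0.080/0.447 = 0.18 change SD
- r = 0.7: 0.239 baseline SD; 0.239/0.775 = 0.31 change SD

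Against the assumed 0.8 change SD, that is 22% to 39% of the effect.

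**The case against.** The SAP's grouping follows the stated design: section C stratifies by level and completeness, Aim 2 asks which injury characteristics predict outcome, and Aims 2a to 2c are not symptom-specific. The planned ANOVA answers those aims and should stay. Level is also closer to the lead hypotheses than it first appears, because they define their populations by sphincter state, and section B links level to sphincter state directly. Both points stand. What they leave open is that level is imperfect for sphincter state and does not separate the symptoms on which the endpoints are measured.

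Four stronger readings are tempting, and the documents do not support them.

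- *The problem vanishes only if every trainee has FI.* Equal change in the other trainees would also remove the dilution, though not for FI episodes in people who have none. Nor would FI in every trainee guarantee the hypothesised population: section B recognises incontinence from overflow and from rectal urgency, without a weak sphincter.
- *This concerns only what is estimated and leaves power untouched.* That needs trainees without FI to show no variability in change. With SD 1 and 10 of 20, power is 34% against 62%.
- *Reporting by group gives a clean effect.* There is no untrained control arm, and selecting on the baseline score adds regression to the mean.
- *The protocol contradicts itself on completeness.* Section B says "we are planning on enrolling all non-ambulatory SCI subjects with complete or incomplete injuries (ASIA A, B, C or D", while Part 2 lists ASIA B to D. This reads naturally as Part 1 enrolling all and Part 2 taking the incomplete subset.

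**Conclusion.** The point holds as a gap between the lead hypotheses and the analysis. Followed as written, the SAP answers Aims 2a to 2c but yields case-mix averages for FI and constipation outcomes, not the effects that the lead hypotheses state. In the illustration the average is half the effect in FI subjects (0.40 against 0.80 SD) at 10 of 20 and three quarters of it at 15 of 20. This rests on an assumed 0.8 SD effect and no average change in the other trainees. The actual size cannot be set from the documents, because the FI share is not given. Power and coverage depend further on the variability of the other trainees, so no single figure should be quoted for them. In a 20-person uncontrolled pilot this is an inexpensive improvement to the plan and does not invalidate the planned analysis.

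The FI-only wording under Recruitment and Enrollment conflicts with the either-symptom wording in section B, Study Population and Part 1. If it governed, the dilution from trainees without FI would go, but the constipation hypothesis would still have no matching group.

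**What to change.** Keep the planned ANOVA for Aims 2a to 2c, and add to the SAP, before pre-post data are examined:

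1. **Groups.** Define baseline FI and constipation groups, overlap allowed, by one stated rule. The symptom reported at screening is preferable, if the screening questionnaire (Appendix 1, not in the text available here) records it. Give the sphincter features named in section A (external sphincter strength, resting tone, RAIR) as a second classification with its own stated rule, so that it is clear what happens when symptom and manometry disagree.
2. **Reporting.** Give pre-post change with 95% CIs for FI episodes, Wexner score, bowel survey score and squeeze pressure in the FI group, and for constipation symptoms and RAIR in the constipation group. State the number in each group and in the overlap. Label these as descriptive pilot estimates, not tests.
3. **Limitations.** State the wider intervals and, if groups are chosen on a baseline score, the regression to the mean shown above. Grouping on the screening symptom instead of the baseline Wexner score would lessen the latter.

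Separately, reconcile the passages on which symptoms qualify a subject for entry.

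The change is SAP wording only. Manometry and surveys are already repeated after the in-house training and again after the home exercises (Protocol, Part 2), so no new visits or measurements are needed.

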Fifty subjects will first undergo an SCI ASIA Impairment examination performed by a trained SCI research staff member. Upon completion of the ASIA exam to determine completeness/incompleteness of the injury, all subjects will undergo an anorectal manometry and a baseline assessment of level of constipation or frequency of FI. Approximately 15 AB subjects will also undergo anorectal manometry and serve as a comparison group for baseline measures. The 10 Question Bowel Survey, and Wexner’s Incontinence Scale (Appendix 2) will be administered to both groups. All SCI subjects will also complete 3 additional surveys: SCI Bowel Management QOL, SCI Bladder Complication, and SCI Bladder Management. These surveys will test the sensitivity of the SCI-QOL measures within the context of existing interventional studies by comparing it with the legacy tool(s) being used. All manometry studies for AB and SCI subjects will be scheduled for bowel care days (post bowel care routine) to decrease the incidence of incidental bowel movement. After informed consent has been obtained, all subjects will be asked to arrive on the morning of the scheduled visit to the SCI Research Unit (Suite 7A-13). Subjects will be transferred onto a commode bed and asked to lie on their left side. A sheathed and lubricated probe with an inflatable balloon attached to the distal end, will be inserted into the rectum. The probe will be outfitted with an EMG sensor in order to monitor pelvic floor muscle activity. The manometric study will last for approximately 45 minutes and will consist of the following tests, during which muscle activity and pressure will be monitored.

1. Baseline assessment- after a period of acclimation, subjects will be asked to relax for a 30 second period, in which they will be asked to refrain from performing any squeezing or bearing down maneuvers.
2. Squeezing maneuvers- subjects will be asked to squeeze their sphincter muscles as if they were retaining stool. Squeezing maneuvers will be performed until 3 consistent attempts are made.
3. Bearing down maneuvers- subjects will be asked to bear down as though they were attempting to move their bowels. Bearing down maneuvers will be performed until 3 consistent attempts are made.

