All training session will take place at the SCI Research Unit (Suite 7A-13). Subjects will be transferred onto a commode bed and asked to lie on their left side. A small disposable electromyography (EMG) plug electrode will be inserted into the rectal cavity, which will permit the subject to watch the trace of pelvic floor muscle activity (Figure 1) at rest, during voluntary contraction (squeeze) and during relaxation (bearing down). The subject will be asked to try to follow the visual prompts for approximately 30 minutes; for example, in the visual provided in Figure 1, the subject will be asked to try to guide the fish through the stream by voluntarily contracting and relaxing their pelvic floor muscles. These tracings will increase in levels of difficulty and complexity, as the subject is able accurately (< 10 percent error) reproduce the tracing in the level, within set times.

[figure not shown]
Response to balloon distension will be performed following the tracing exercises. The EMG

Figure 1: Biofeedback Visual

probe will be removed, and a pressure probe with EMG sensor will be inserted. An inflatable balloon will be at the distal end of each probe. The balloon will be distended to until an urge to defecate occurs or to a maximum of 150 ccs. The subject will be asked try and retain the balloon by squeezing the pelvic muscles. Based on each individual subject’s baseline abilities, between 5- 50 squeezes will be attempted/performed during the first sessions. Repetitions and target pressures will be increased from session to session based on individual gains. No more than 15 minutes will be spent on balloon distension trials. These sessions will be performed twice a week for 6 weeks. After 6 weeks of in-house training, each subject will undergo another manometric and survey study identical to Part 1 of the study. Subsequently, each subject will be sent home with a personalized training schedule, and will be asked to perform repetitions of squeezing and bearing down maneuvers two times a week. Each typical at home exercise program should last 30 minutes. After 6 weeks of home exercises, a third manometric study will be performed, and bowel surveys will be administered.

Study Timeline

We are proposing three year study duration.

Years 1 and 2: 25 SCI subjects for anorectal manometry; 5 AB subjects; and 10 incomplete SCI subjects for biofeedback training (per year).

Year 3: Results dissemination.

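### The SAP models two visits (Pre, Post) but the protocol schedules three, and neither document says whether Post is week 6 or week 12

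*SAP*

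**What the plan says.** The SAP is a single paragraph. Its model for the training effect is an "analysis of variance (ANOVA) with repeated measures on visit (Pre, Post) will be performed", with groups defined by level and completeness of injury. Significance is set at P≤0.05. Descriptive statistics with 95% confidence intervals are promised without reference to visit.

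The protocol gives Part 2 subjects three assessments:

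- **Baseline** (section C, Part 1): "all subjects will undergo an anorectal manometry and a baseline assessment of level of constipation or frequency of FI".
- **Week 6** (section C, Part 2): of the in-house biofeedback, "These sessions will be performed twice a week for 6 weeks"; then "After 6 weeks of in-house training, each subject will undergo another manometric and survey study identical to Part 1 of the study".
- **Week 12** (section C, Part 2): "After 6 weeks of home exercises, a third manometric study will be performed, and bowel surveys will be administered".

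Three other statements bear on the meaning of Post. The last paragraph of section B says "we are proposing the use of a 12 week biofeedback training", and later in the same paragraph "Anorectal motility pre to post biofeedback training will be performed". Aim 2a in section A refers to pressures "performed during anorectal manometric studies pre-post treatment". None of them names a week.

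**The concern.** A two-level visit factor cannot hold three visits. An analyst following the SAP must leave one follow-up out of the model, or merge the two in some way the SAP does not describe.

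The choice changes the question. Week 6 minus baseline estimates the change over supervised, in-house biofeedback. Week 12 minus baseline estimates the change over the whole programme, half of which is home exercise. Gains could fade or build in the home phase, so the two contrasts could lead to different conclusions. Because the plan does not fix the choice, it can be made after both results are known, with no allowance for having had two chances.

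**Working it through.** The documents give no power, effect size, SD or sample-size derivation, so there is no stated figure to reproduce. The finding rests on step 1; the other steps show its size.

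**1. Visits against factor levels.** The protocol has 3 assessments (weeks 0, 6 and 12) and the SAP's visit factor has 2 levels. Part 2 recruits 20 subjects, giving 20 × 2 = 40 follow-up studies if all complete. A Pre/Post model uses 20 of them, so 20/40 = 50% of the follow-up studies have no specified test.

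**2. Can Post be inferred?**

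| Text | Points to |
|---|---|
| Protocol section B: 12-week training, motility measured before and after it | Week 12 |
| Protocol section C, Part 2: biofeedback sessions last 6 weeks, with a full repeat assessment straight after | Week 6 |
| Protocol section A, aim 2a: before and after treatment | Neither |
| SAP: Post | Neither |

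Whichever row is preferred, one follow-up stays outside the model.

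**3. Degrees of freedom.** With N subjects, g groups and k visits, the visit test has (k−1) and (N−g)(k−1) df. Part 2 takes incomplete injuries only, so g = 2 (upper and lower motor neuron). With N = 20:

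- k = 2: F(1, 18).
- k = 3: F(2, 36).

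**4. False-positive chance if either follow-up may serve as Post.** Assumptions: 20 completers, normal data, no true effect, and paired t-tests of week 6 and week 12 against baseline, each two-sided at 0.05. (An ANOVA F-test with 1 numerator df is the square of a two-sided t, so this matches the SAP's test.) For two independent tests the figure would be 1 − 0.95² = 0.0975, and the upper bound is 0.05 + 0.05 = 0.10. Here the two contrasts share a baseline, so they are correlated. With equal variances, and r01, r02 and r12 the baseline–week 6, baseline–week 12 and week 6–week 12 correlations, the two change scores correlate at

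(1 + r12 − r01 − r02) / √[(2 − 2·r01)(2 − 2·r02)].

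If all three correlations equal r, this is (1 − r)/(2 − 2r) = 0.5 whatever r is, which is why the first row barely moves. Simulation (400,000 runs per setting):

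| Correlations (r01, r02, r12) | P(either P≤0.05) |
|---|---|
| Equal: 0.3, 0.5, 0.7 or 0.9 | 0.091 to 0.092 |
| 0.5, 0.25, 0.5 | 0.088 |
| 0.7, 0.49, 0.7 | 0.087 |
| 0.5, 0.5, 0.8 | 0.080 |
| 0.6, 0.4, 0.8 | 0.078 |
| 0.7, 0.7, 0.9 | 0.076 |

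A single contrast named in advance gives 0.049 to 0.051. Holm over the two contrasts (smaller P≤0.025) gives 0.039 to 0.048. Adding a two-group factor, split 10/10 or 14/6 with r = 0.5 or 0.7, leaves the unadjusted figure at 0.091 to 0.092.

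**5. Detectable change at 80% power** (noncentral t, in SDs of the change score):

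- One group, n = 20, alpha 0.05: 0.66 SD.
- Same, alpha 0.025 (first Holm step): 0.74 SD.
- Unweighted visit effect with an assumed 14/6 group split: effective n = 4/(1/14 + 1/6) = 16.8, and with 18 df at alpha 0.05, 0.72 SD.

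**The case against.** The strongest reply is that Post naturally means week 12. Six weeks in-house plus six weeks at home makes the 12 weeks of section B, and the home phase runs on a personalised training schedule, so it can be counted as training. Week 6 would then be an intermediate visit, for which descriptive statistics with confidence intervals may be enough in a non-randomized pilot. On that reading there is no choice of visit and no error inflation.

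Much of this stands. Week 12 is the more natural reading, the two durations are arithmetically compatible, and a visit may be reported descriptively if the plan says so. But the SAP does not say so. The week 12 reading also takes the one assessment made directly after the biofeedback sessions out of the only model specified. Nor does pilot status remove the need: section A sets an aim of assessing efficacy, and the SAP sets a significance level in advance.

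Three limits are also fair. The 9.1% figure belongs to equal correlations and is near the top of the range; if the follow-ups resemble each other more than they resemble baseline, it is nearer 8%. The 0.66 SD figure is a one-group or balanced case. And fixing the visit controls error only per outcome: Part 1 lists 16 manometric parameters and five surveys, and neither document names a primary outcome.

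The SAP (March 2013) predates the protocol (October 2016). Whether the third assessment was added between those dates cannot be told from the documents, but the two versions disagree either way.

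**Conclusion.** The concern holds and should be fixed. The mismatch of two levels against three assessments can be read directly from the texts and needs no assumption. Its consequence is that half the planned follow-up studies have no specified inferential analysis, and that the choice between two different estimands stays open until after the data are seen.

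The error rate of 7.6% to about 9.1% per outcome, against 5%, is a conditional risk. It applies only if either visit may be chosen as Post without adjustment, and it assumes 20 completers, normal data and correlations that the documents do not give. Nothing in the documents shows that the choice would be made that way, and the conclusion does not depend on this figure.

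**What to change.** In the SAP:

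1. Replace the two-level visit factor with three levels: baseline, week 6 and week 12. A linear mixed model using all available visits is preferable, since a subject who misses one visit still contributes the others. A repeated-measures ANOVA with a sphericity correction would also do.
2. Name one primary contrast before the data are analysed: week 6 minus baseline if the question is the in-house phase, or week 12 minus baseline if it is the full programme. That choice belongs to the sponsor.
3. Label the remaining contrasts, including week 12 minus week 6, as secondary with a stated multiplicity rule (Holm, for example) or as exploratory.

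In the protocol, reconcile the 12-week training in section B with the 6 weeks of sessions followed by home exercise in section C, so that both documents use one definition of the end of training.

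The cost is wording and slightly more analysis. There are no new visits, data or patients. One named contrast keeps the full 0.05 for that outcome, with a detectable change of 0.66 SD in the one-group case (0.72 SD at the assumed 14/6 split). Making both follow-up contrasts co-primary under Holm would raise the one-group figure to 0.74 SD at the first step.
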